10.3.2 Pharmacokinetic Statistical Methodology

Rosuvastatin

Log-transformed C_{max} and $AUC(0-\infty)$ of rosuvastatin will be evaluated in a linear mixed-effects model with fixed effects for treatment and a random effect for participant. The treatment differences will be back-transformed to present the ratios of geometric least squares means and the corresponding 90% CIs. The test treatment is rosuvastatin in the presence of selpercatinib, and reference treatment is rosuvastatin alone.

The parameter t_{max} of rosuvastatin will be analyzed non-parametrically. Estimates of the median for each treatment, median of the within-participant differences, approximate 90% CI for the difference, and p-value from the Wilcoxon signed-rank test will be calculated.

Example of the SAS code that will be used are as follows:

Mixed Model Analysis

CCI

Signed rank test (tmax)

CCI

Coproporphyrin 1

The effect of a single dose of selpercatinib (Day 5) on plasma coproporphyrin I, a biomarker of OATP inhibition in healthy participants, will be explored.

Log-transformed C_{max} and $AUC(0-24)$ of coproporphyrin I will be evaluated in a linear mixed-effects model with fixed effects for treatment and a random effect for participant. The treatment differences will be back-transformed to present the ratios of geometric least squares means and the corresponding 90% CIs. The test treatment is coproporphyrin I in the presence of rosuvastatin and selpercatinib (Day 5), and reference treatment is coproporphyrin I in the presence of rosuvastatin (Day 1).

The SAS code will be similar to that above.

Selpercatinib

The PK parameters of selpercatinib will be summarized and listed. No inferential statistical analyses are planned.

10.4 Safety and Tolerability Assessments

10.4.1 Adverse events

Where changes in severity are recorded in the Case Report Form (CRF), each separate severity of the AE will be reported in the listings, only the most severe will be used in the summary tables. A pre-existing condition is defined as a condition that starts before the participant has provided written informed consent and is ongoing at consent. A non-treatment emergent AE is defined as an AE which starts after informed consent but prior to dosing. A treatment-emergent AE is defined as an AE which occurs postdose or which is present prior to dosing and becomes more severe postdose.

All AEs will be listed. Treatment-emergent AEs will be summarized by treatment, severity and relationship to the study drug. The frequency (the number of AEs, the number of participants experiencing an AE and the percentage of participants experiencing an AE) of treatment-emergent AEs will be summarized by treatment, Medical Dictionary for Regulatory Activities (MedDRA) (version is documented in the Data Management Plan [DMP]) system organ class and preferred term. The summary and frequency AE tables will be presented for all

causalities and those considered related to the study drug by the investigator. Any serious AEs will be listed.

Discontinuations due to AEs will be listed.

Adverse events of special interest include hypersensitivity, liver injury, QT prolongation, and hypertension. Any adverse events of special interest will be listed.

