#### **4.4. End of Study Definition**

The end of the study is defined as the last scheduled procedure shown in the SoA (Section 1.3) for the last participant in the study.

A participant is considered to have completed the study if the participant has completed the treatment period of the study and the follow-up procedures as shown in the SoA (Section 1.3).

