### **9.3.3. Secondary Endpoint Analysis: Safety Analyses**

All safety analyses will be made using the Safety Population.

The incidence of TEAEs and SAEs will be reported separately with respect to the dose date for selpercatinib (i.e., separate events and percentages will be reported for AEs pre-selpercatinib and post-selpercatinib).

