IMP	Investigational Medicinal Product (see also "investigational product") A medicinal product which is being tested or used as a reference, including as a placebo, in a clinical trial.
informed consent	A process by which a participant voluntarily confirms their willingness to participate in a particular study, after having been informed of all aspects of the study that are relevant to the participant's decision to participate. Informed consent is documented by means of a written, signed and dated informed consent form.
investigational product	A pharmaceutical form of an active ingredient or placebo being tested or used as a reference in a clinical trial, including products already on the market when used or assembled (formulated or packaged) in a way different from the authorized form, or marketed products used for an unauthorized indication, or marketed products used to gain further information about the authorized form. See also "IMP."
OATP1B1	organic anion transporting polypeptide 1B1
participant	Equivalent to CDISC term "subject": an individual who participates in a clinical trial, either as recipient of an investigational medicinal product or as a control
PC	product complaint
PK	pharmacokinetics
QTc	corrected QT interval
QTcB	QT corrected using Bazett's formula
QTcF	QT corrected using Fridericia's formula
SAE	serious adverse event

screen	The act of determining if an individual meets minimum requirements to become part of a pool of potential candidates for participation in a clinical study.
SoA	Schedule of Activities
t1/2	terminal elimination half-life
TBL	total bilirubin
TEAE	Treatment-emergent adverse event: An untoward medical occurrence that emerges during a defined treatment period, having been absent pretreatment, or worsens relative to the pretreatment state, and does not necessarily have to have a causal relationship with this treatment.
tmax	time to maximum drug concentration
ULN	upper limit of normal

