3. INTRODUCTION

This SAP has been developed after review of the Clinical Study Protocol (final version dated 03 April 2023).

This SAP describes the planned analysis of the safety, tolerability and pharmacokinetic (PK) data from this study. A detailed description of the planned Tables, Figures, and Listings (TFLs) to be presented in the clinical study report (CSR) is provided in the accompanying TFL shell document.

The intent of this document is to provide guidance for the statistical and PK analyses of data. In general, the analyses are based on information from the protocol, unless they have been modified by agreement with Eli Lilly and Company. A limited amount of information concerning this study (e.g., objectives, study design) is given to help the reader's interpretation. This SAP must be finalized prior to first participant visit. When the SAP and TFL shells are agreed upon and finalized, they will serve as the template for this study's CSR.

This SAP supersedes the statistical considerations identified in the protocol; where considerations are substantially different, they will be so identified. If additional analyses are required to supplement the planned analyses described in this SAP, they may be performed and will be identified in the CSR. Any substantial deviations from this SAP will be agreed upon with Eli Lilly and Company and identified in the CSR. Any minor deviations from the TFLs may not be documented in the CSR.

This SAP is written with consideration of the recommendations outlined in the International Conference on Harmonisation (ICH) E9 Guideline entitled Guidance for Industry: Statistical Principles for Clinical Trials¹ and the ICH E3 Guideline entitled Guidance for Industry: Structure and Content of Clinical Study Reports².

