12. CHANGES FROM THE PROTOCOL SPECIFIED STATISTICAL ANALYSES

There were no changes from the protocol specified statistical analyses.

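### The by-treatment TEAE table sets 4 days on rosuvastatin alone against 7 to 10 days on the combination, and the SAP text plans no equal-window summary

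*SAP*

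**What the plan says.** Four parts of the plan fix how adverse events are counted.

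- **Definition.** SAP 10.4.1: "A treatment-emergent AE is defined as an AE which occurs postdose", or one already present that worsens after dosing. No closing time is given.
- **Measure.** SAP 10.4.1: "Treatment-emergent AEs will be summarized by treatment, severity and relationship to the study drug". The frequency tables, also by treatment, give "the number of AEs, the number of participants experiencing an AE and the percentage of participants experiencing an AE". The text has no time restriction and no adjustment for length of observation.
- **Split.** Protocol 9.3.3: "separate events and percentages will be reported for AEs pre-selpercatinib and post-selpercatinib". The SAP text does not itself say how an event is assigned to a treatment, so the Day 5 split is taken from here.
- **Collection.** Protocol 8.3.1 collects adverse events from the start of intervention until participation has ended. Protocol 4.1 places the follow-up visit 7 to 10 days after the Day 5 dose. If the participant cannot attend, a phone call covers adverse events.

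The protocol glossary (Appendix 8) words the definition differently: "An untoward medical occurrence that emerges during a defined treatment period". It does not say which days that period covers.

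**The concern.** Each participant contributes to both columns, and protocol 4.2 gives safety comparisons as one reason for letting participants act as their own control. Incidence of TEAEs and SAEs is the secondary endpoint. A reader will naturally set the combination column beside the rosuvastatin-alone column. If one column simply watches people for longer, it gathers more unrelated events, and the difference can look like an effect of adding selpercatinib.

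Unrelated events do reach such tables. In the sponsor's single-dose study of 224 healthy participants (protocol 2.3), COVID-19 was the second most frequent TEAE, in 13 participants (13/224 = 5.8%).

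**Working it through.** **Window lengths**

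- The follow-up timing in protocol 4.1 reproduces: 12 − 5 = 7 and 15 − 5 = 10 days after the Day 5 dose.
- Rosuvastatin alone: 5 − 1 = 4 days, which matches the 4 days between doses in protocol 4.2.
- Combination, in-unit part: 8 − 5 = 3 days to discharge. Outpatient part: 7 − 3 = 4 to 10 − 3 = 7 days.

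**Event counts with no drug effect**

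Assume a constant hazard, and let c be the share of outpatient events captured. The hazard cancels:

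ratio (combination/alone) = (3 + c × outpatient days) / 4

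- c = 1: 7/4 = 1.75 to 10/4 = 2.5.
- c = 0.5: (3 + 2)/4 = 1.25 to (3 + 3.5)/4 = 1.63.
- The ratio equals 1 at c = 1/4 (4 outpatient days) or c = 1/7 (7 outpatient days). Below that it falls towards 3/4 = 0.75.

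The documents give no value for c. An adverse event review is scheduled at follow-up, so near-zero capture is not what the plan intends.

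**Participants with at least one event**

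Incidence = 1 − exp(−h × days). The documents give no daily hazard h, so 1% to 4% per day is assumed. With full capture:

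- h = 1%: 3.9% alone; 6.8% to 9.5% combination; ratio 1.72 to 2.43.
- h = 2%: 7.7% alone; 13.1% to 18.1% combination; ratio 1.70 to 2.36.
- h = 4%: 14.8% alone; 24.4% to 33.0% combination; ratio 1.65 to 2.23.

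With 50% capture, the ratio over the same hazards is 1.23 to 1.60.

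**Scale against chance**

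With 28 participants and h = 2%, the expected numbers are 2.2 alone against 3.7 to 5.1 on the combination with full capture, a difference of 1.51 to 2.92. Dividing by √(28(p₁q₁ + p₂q₂)) gives 0.66 to 1.18 standard deviations. At 50% capture the difference is 0.51 to 1.26, or 0.24 to 0.56 standard deviations. This treats the two columns as independent, although the same people are in both.

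**After the change**

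With 72 hours after each dose the windows are 3 days and 3 days. The null ratio is 3/3 = 1 whatever h or c is, because both windows fall in the unit: Day 1 to Day 4, and Day 5 to Day 8, where the schedule of activities places the 72-hour ECG.

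**The case against.** **The table is descriptive.** The objective is to describe safety on the combination, SAP 10.4.9 plans no inference, and following the combination to Days 12 to 15 is useful for that purpose. This stands. It is why the planned table should be kept and why the point is minor. It does not remove the by-treatment layout or the own-control rationale in protocol 4.2.

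**The size rests on assumptions.** This also stands. Hazard, capture and constancy over time are not in the documents, and protocol 2.3 gives no observation time from which to derive a rate. Events clustered soon after dosing would shrink the distortion. The unequal window lengths themselves do not depend on these assumptions.

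**Other outputs help.** All adverse events are listed, and there are tables restricted to related events. With about 28 participants, late events can be picked out if onset dates are listed. The TFL shells were not available and may already set attribution or denominators. This is partial relief: a reader would have to rebuild the counts, and relatedness is judged open-label.

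**72 hours is a choice.** It is 72/19.6 = 3.7 half-lives at the upper end of the selpercatinib range in protocol 2.2, and 72/39.8 = 1.8 at the upper end of the rosuvastatin range in protocol 4.2. It does not cover all exposure, so later events must be shown too. Its merit is observation in the unit after both doses; a 96-hour window would run past Day 8.

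**Stronger readings that the documents do not support.** Protocol 4.4 requires a completer to have "completed the treatment period of the study and the follow-up procedures". A reader might combine this with the glossary to end the TEAE window at Day 8 discharge, giving 4 against 3 days and leaving the direction of the imbalance open. That is only one possible reading. The glossary entry is generic, neither passage names Day 8 as a cut-off, protocol 9.3.3 splits events only at the selpercatinib dose, and collection continues through follow-up.

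A reader might also set the SAP 3 undertaking, "where considerations are substantially different, they will be so identified", against SAP 12, "There were no changes from the protocol specified statistical analyses", and infer an undeclared change. Without a dated protocol window, no substantive difference is shown, and SAP 3 states that it supersedes the protocol's statistical considerations.

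Finally, the single pretreatment baselines for laboratory tests and vital signs (SAP 10.4.3 and 10.4.4) might look like the same problem. They are a legitimate choice and no error is shown.

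**Conclusion.** The point holds as a minor one. Under the SAP definition and the protocol's split at Day 5, crude TEAE counts and percentages are reported over 4 days for rosuvastatin alone and 7 to 10 days for the combination, so they are not like for like. If there is no drug effect, hazard is constant and outpatient capture is full, the combination column is expected to hold 1.75 to 2.5 times as many events. At an assumed 2% per day, that is about 1.5 to 2.9 extra participants of 28, at most about 1.2 standard deviations of chance variation. The shift is modest but systematic, and it can be removed with data already planned. The primary pharmacokinetic analysis is unaffected. That no equal-window summary is planned can be confirmed only for the protocol and SAP text.

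**What to change.** In SAP 10.4.1, keep the planned table and add a TEAE summary restricted to onset (or worsening) within 72 hours of each dose. Use the number of participants dosed in that period as denominator, and show later-onset events separately. State in the SAP how an event is assigned to a treatment and when the window closes, and align the protocol glossary's treatment-period wording with the SAP definition.

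The cost is a few lines of SAP text and a few table columns or rows; no new data are needed. There are three downsides. The output is slightly longer. Events after 72 hours, including those from 72 to 96 hours on rosuvastatin alone, fall outside the matched comparison. Period effects remain confounded with treatment in a fixed sequence, so equal windows remove only the difference in observation time. The TFL shells should be checked first in case they already cover part of this.

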10.4.2 Concomitant medication

Concomitant medication will be coded using the WHO drug dictionary (version is documented in the DMP). Concomitant medication will be listed.

10.4.3 Clinical laboratory parameters

All clinical chemistry and hematology data and their changes from baseline will be summarized by time point, where baseline is defined as Day -1, and listed. Urinalysis data will be listed. Additionally, clinical chemistry, hematology and urinalysis data outside the reference ranges will be listed and flagged on individual participant data listings.

Values recorded as $< x$, $\leq x$, $> x$, or $\geq x$ will be displayed in the listings as recorded. For the calculation of summary statistics, $< x$ and $\leq x$ values will be set to $0.5 \times x$, whereas $> x$ and $\geq x$ values will be set to $1.1 \times x$.

10.4.4 Vital signs

Vital signs data will be summarized by time point together with changes from baseline, where baseline is defined as the Day 1 predose assessment. Figures of mean vital signs and mean changes from baseline will be presented over time.

Values for individual participants will be listed.

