### 1.3. Schedule of Activities (SoA)

Study Procedure	Screening	Treatment										FU/ED	Comments
		-1	1	2	3	4	5	6	7	8	12 to 15		
Study Day	-42 to -2												
Informed consent	X												
Medical history and demographics	X	X											
Admission to CRU		X											
Discharge from CRU											X		
Outpatient visit	X											X	
Participant eligibility	X	X											
Height and weight	X	X										X	Height: screening only.
Physical examination		X										X	Day -1: Full examination. Day 8: Symptom-driven examination.
Pregnancy test	X	X										X	Serum pregnancy test: screening. Urine pregnancy test: all other time points.
FSH	X												See Section 10.4.1.
Serology	X												
Clinical laboratory tests	X	X			X		P		X		X		
12-lead ECG (hr)	X		P				P, 2, 4	24	48	72	X		
Vital signs and body temperature (supine) (hr)	X	X	P	24	X	X	P, 1, 2	24	X	X	X		Temperature: screening and Day -1.
Ethanol test	X	X											
Urine drug screen	X	X											

Study Procedure	Screening	Treatment										FU/ED	Comments
		-42 to -2	-1	1	2	3	4	5	6	7	8		
Study Day	-42 to -2												
Genetic blood sample for screening	X												
Pharmacogenetic blood sample for storage			P										
Rosuvastatin administration				X					X				
Selpercatinib administration									X				
Rosuvastatin PK samples (hr)													
Selpercatinib PK samples (hr)													
Plasma coproporphyrin I samples (hr)													
Adverse events			X	X	X	X	X	X	X	X	X		
Concomitant medications	X	X	X	X	X	X	X	X	X	X	X		

Abbreviations: CRU = clinical research unit; ECG = electrocardiogram; ED = early discontinuation; FSH = follicle stimulating hormone; FU = follow-up;

hr = hour; P = predose; PK = pharmacokinetics.

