### 2.2. Background

Selpercatinib (LY3527723, Retevmo®) is a orally available, highly selective, adenosine triphosphate (ATP)-competitive small molecule inhibitor of the *REarranged during Transfection (RET)* gene receptor tyrosine kinase (RTK) approved by the FDA for the treatment of

- adult patients with locally advanced or metastatic non-small cell lung cancer (NSCLC) with a *RET* gene fusion, as detected by an FDA-approved test
- adult and pediatric patients 12 years of age and older with advanced or metastatic medullary thyroid cancer (MTC) with a *RET* mutation, as detected by an FDA-approved test, who require systemic therapy
- adult and pediatric patients 12 years of age and older with advanced or metastatic thyroid cancer with a *RET* gene fusion, as detected by an FDA-approved test, who require systemic therapy and who are radioactive iodine-refractory (if radioactive iodine is appropriate)
- adult patients with locally advanced or metastatic solid tumors with a *RET* gene fusion that have progressed on or following prior systemic treatment or who have no satisfactory alternative treatment options

Across clinical studies, single oral doses of selpercatinib were administered over a range of 20 to 720 mg. In studies (LOXO-RET-18017 and LOXO-RET-18026), multiple oral doses of 160 mg/day selpercatinib were administered orally twice daily for 10 days in healthy participants.

In healthy participants, the median (range) time to maximum drug concentration ( $t_{max}$ ) of selpercatinib is 2 (1.5 to 6.0) hours and selpercatinib is eliminated with a mean (range) terminal elimination half-life ( $t_{1/2}$ ) of 13.6 (9.82 to 19.6) hours.

More detailed information about the PK and absorption, distribution, metabolism, and excretion properties of selpercatinib may be found in the Investigator's Brochure (IB).

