## 2.3. Benefit/Risk Assessment

There is no anticipated therapeutic benefit for the participants in this study. However, participants may benefit from the screening procedures (through detection of unknown health issues) even if they receive no therapeutic benefit from the study.

The single dose of selpercatinib to be given in this study is 160 mg (2 × 80-mg capsules), as it is the highest approved dose by the FDA. The safety profile of selpercatinib shows that selpercatinib is very well tolerated in healthy participants and is clinically manageable, with low rates of study drug discontinuation due to adverse events (AEs). As outlined in the IB, the most common toxicities associated with selpercatinib are monitorable and reversible, and include dry mouth, diarrhea, hypertension, fatigue, constipation, aspartate aminotransferase (AST)/ alanine aminotransferase (ALT) elevation, headache, nausea, edema peripheral, abdominal pain, rash, electrocardiogram (ECG) QT prolonged, cough, vomiting, dyspnea, and increased blood creatinine. Adverse events of special interest include hypersensitivity, liver injury, QT prolongation, and hypertension. In a recently completed DDI study with dabigatran in healthy participants (Study J2G-MC-JZJV), only 1 treatment-emergent adverse event (TEAE) considered to be related to selpercatinib was reported (dyspepsia). In a single 160-mg dose, crossover bioequivalent study in 224 healthy participants (Study J2G-MC-JZJZ), the most frequently reported TEAEs following dosing was headache (20 events in 16 participants) followed by COVID-19 (13 events in 13 participants). Four AEs of ALT increased and 2 AEs of AST increased were reported, all were mild in severity and resolved by the end of the study.

More detailed information about the known and expected benefits and risks and reasonably expected AEs of selpercatinib may be found in the IB.

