### 4.2. Scientific Rationale for Study Design

To allow each participant to act as their own control for safety and PK comparisons, a fixed sequence design has been selected. This study will be open label as the study primary endpoint PK measures are objective rather than subjective.

Based on the  $t_{1/2}$  of rosuvastatin from label (19 hours; Crestor Prescribing Information, 2020) or observed from Study J2N-MC-JZNW (geometric mean of 8.21 hours with range of 3.02 to 39.8 hours), a period of 4 days between rosuvastatin doses is considered sufficient time for the study intervention to washout.

The PK of rosuvastatin will be evaluated after a single dose on Day 1 and again on Day 5, coadministered simultaneously with selpercatinib, to assess the effect of selpercatinib on intestinal BCRP.

Conducting the study in healthy participants mitigates the potential confounding effects of any disease state, other medical conditions, and concomitant medications in patients.

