10. STATISTICAL METHODOLOGY

10.1 General

Data listings will be provided for all data that is databased. Summary statistics and statistical analysis will only be presented for data where detailed in this SAP. For continuous data, summary statistics will include the arithmetic mean, arithmetic standard deviation (SD), median, minimum, maximum and number of observations; for log-normal data (e.g. the PK parameters: AUCs and C_{max}) the geometric mean and geometric coefficient of variation (CV%) will also be presented. For categorical data, frequency count and percentages will be presented. Data listings will be provided for all participants up to the point of withdrawal, with any participants excluded from the relevant population highlighted. Summary statistics and statistical analyses will generally only be performed for participants included in the relevant analysis population. For the calculation of summary statistics and statistical analysis, unrounded data will be used.

For change from baseline summary statistics, each individual change from baseline will be calculated by subtracting the individual participant’s baseline value from the value at that time point. The individual participants’ change from baseline values will be used to calculate the summary statistics (arithmetic mean, arithmetic SD, median, minimum, maximum and number of observations) using a SAS procedure such as Proc Univariate.

Data analysis will be performed using SAS® Version 9.4 or greater.

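### Do the safety tables need changes measured from the Day 5 pre-dose value as well as from the pre-drug baselines?

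*SAP*

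**What the plan says.** SAP 10.4.4 (Vital signs) summarises values and changes by time point, "where baseline is defined as the Day 1 predose assessment". It also plans figures of mean values and mean changes over time, and a listing of individual values. SAP 10.4.3 (Clinical laboratory parameters) does the same for chemistry and haematology, "where baseline is defined as Day -1, and listed"; urinalysis is only listed. Under SAP 10.1, changes are described by mean, SD, median, minimum, maximum and number of observations. SAP 10.1 also sets a limit: "Summary statistics and statistical analysis will only be presented for data where detailed in this SAP". No second baseline is defined in either document.

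The Schedule of Activities (Protocol 1.3) gives these in-residence times:

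| | After rosuvastatin alone | Day 5 pre-dose | After rosuvastatin plus selpercatinib |
|---|---|---|---|
| Vital signs | Day 2 (24 h), Day 3, Day 4 | yes | Day 5 at 1 h and 2 h, Day 6 (24 h), Day 7, Day 8 |
| Laboratory tests | Day 3 | yes | Day 7 |

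On Day 1 itself vital signs are taken only before the dose. Protocol 9.3.3.2 asks for listings and standard descriptive statistics, and allows further analysis if the data warrant it. SAP 10.4.9 plans no inferential safety analysis.

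**The concern.** The secondary objective is to describe the safety of rosuvastatin given with selpercatinib, and Protocol 2.3 states: "Adverse events of special interest include hypersensitivity, liver injury, QT prolongation, and hypertension". A change measured from Day 1 or Day -1 also contains any drift or rosuvastatin effect that arose before Day 5. The Day 5 readings at 1 h and 2 h are the ones nearest the selpercatinib peak (Protocol 2.2 states that the median time to peak "of selpercatinib is 2 (1.5 to 6.0) hours"). They have no Day 1 counterpart, so their only same-day reference is Day 5 pre-dose.

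Because SAP 10.1 restricts summaries to what the SAP details, the separate table shells cannot be assumed to add this change. If it mattered, a reader could see the average same-day change in blood pressure but would need the listings to find its spread or the largest individual rise.

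**Working it through.** There is no plan figure to reproduce. Four checks follow.

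**1. What the planned rows already give.** Let B be the pre-drug baseline, P5 the Day 5 pre-dose value and Y a later value. For each participant (Y − B) − (P5 − B) = Y − P5. The same holds for means when the same participants contribute. Day 5 pre-dose is itself a scheduled time point, so drift up to Day 5 has its own row and can be subtracted.

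**2. Which time points lack a rosuvastatin-alone counterpart.** Six in-residence points follow the Day 5 dose: five for vital signs and one for laboratory tests. Pairing by time since dose:

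- Vital signs: Day 6 with Day 2 (24 h), Day 7 with Day 3, Day 8 with Day 4.
- Laboratory tests: Day 7 with Day 3.

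At these four, (Day 6 − B) − (Day 2 − B) = Day 6 − Day 2, and likewise for the others. One common drug-free baseline thus supports the comparison of the combination with rosuvastatin alone. Two points remain: vital signs at 1 h and 2 h on Day 5. No laboratory test is scheduled on Day 5 after the dose; the Day 7 test comes about 48 h later, so a same-day argument does not reach the laboratory data.

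**3. Direction and size of the difference in spread.** The documents give no SD or correlation, so all inputs here are assumed: SD s = 10 mmHg at each time; r = correlation of readings four days apart; ρ = correlation of readings hours apart, with ρ ≥ r.

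- Planned SD (change from Day 1) = s√(2(1 − r)): 11.0, 8.9 and 6.3 mmHg for r = 0.4, 0.6 and 0.8.
- Same-day SD (change from Day 5 pre-dose) = s√(2(1 − ρ)). At r = 0.6 this is 8.9, 6.3 and 4.5 mmHg for ρ = 0.6, 0.8 and 0.9.
- Ratio of planned to same-day SD = √((1 − r)/(1 − ρ)) = 1.0, 1.4 and 2.0.

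With 28 participants and an assumed mean rise of 3 mmHg, simulation (200,000 trials) gives an expected largest same-day rise of 21.0, 15.7 and 12.0 mmHg for those three values of ρ. The expected maximum in the planned table is 21.0 in all three. For 20 participants the figures are 19.7, 14.8 and 11.4, against 19.7. On these inputs the planned tables overstate the same-day spread.

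**4. Whether Day 5 pre-dose is a cleaner reference.** Protocol 4.2 gives rosuvastatin half-lives of 19 h from the label and, from another study, a "geometric mean of 8.21 hours with range of 3.02 to 39.8 hours". Simple terminal decline over the 96 h between doses leaves 2^(−96/t): 0.03% at 8.21 h, 3.0% at 19 h and 18.8% at 39.8 h. Day 5 pre-dose is therefore not fully drug-free, whereas the planned baselines are. Nor can a change from Day 5 pre-dose separate selpercatinib from the rosuvastatin dose taken with it.

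**The case for a change.** The strongest counter-argument is that the tables do not determine the missing spread. If two changes from baseline have SDs s₁ and s₂ and correlation c, the same-day SD is √(s₁² + s₂² − 2c·s₁s₂), and no table reports c. With both SDs assumed to be 8 mmHg, the result is 11.3 at c = 0, 8.0 at c = 0.5 and 3.6 at c = 0.9. In a constructed set of 28 participants with identical planned summaries, the mean same-day change is 5 mmHg in every pairing, yet its SD runs from 0 to 15.9 mmHg. The protocol also splits adverse events at the selpercatinib dose (9.3.3), so a matching split here would be natural and cheap.

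The algebra stands, but the upper end of that range is not realistic. The two changes share the same Day 1 reading. With equal SDs, c = (1 + ρ − 2r)/(2(1 − r)), which equals 0.5 when ρ = r and rises with ρ. Under ρ ≥ r the same-day SD cannot exceed the planned 8.0 mmHg, whereas 15.9 requires perfectly opposed changes.

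Individual extremes are also covered elsewhere:

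- Individual vital signs are listed, and out-of-range laboratory values are flagged per participant (SAP 10.4.3, 10.4.4).
- Hepatic monitoring triggers apply to each participant and refer to that participant's own baseline (Protocol 8.2.6.1).
- Clinically relevant laboratory changes and clinically significant vital-sign findings are reported as adverse events (Protocol 8.2.4 and Appendix 3), and events of special interest are listed (SAP 10.4.1).

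The table shells were not available, so the absence of such a table means that none is described in the SAP or protocol.

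**Conclusion.** The concern does not hold. The observation is accurate: no described table gives the SD, median, minimum or maximum of change from Day 5 pre-dose. But both baselines are legitimate and no protocol requirement is breached. The mean same-day change is recoverable when the same participants contribute, and the individual values are available.

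Only two of the six post-dose time points lack a rosuvastatin-alone counterpart, and changing the baseline would not supply one. If readings hours apart correlate at least as well as readings four days apart, with similar SDs, the planned spread is an upper bound for the same-day spread. In the illustration it is 1.0 to 2.0 times as large. Those inputs are assumed; without them the spread is undetermined by the tables but still obtainable from the listings.

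The analysis as written gives sound descriptive safety results. No PK conclusion is touched, and extra columns would be a presentation preference.
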